**Table 10 Summary of Analysis to meet primary efficacy objective of HbA1c**

Analysis type	Estimand	Missing Data Assumption	Imputation Method	Analysis set
Repeated measures mixed model of $\Delta$ HbA1c to Week 24 (prior to rescue and treatment discontinuation) a	Difference in outcome improvement at Week 24 without rescue and without treatment discontinuation.	MAR	No imputation	FAS a
Repeated measures mixed model of $\Delta$ HbA1c to Week 24 (prior to rescue and treatment discontinuation) b	Difference in outcome improvement at Week 24 without rescue and without treatment discontinuation. For PP analysis set only.	MAR	No imputation	PP b
Repeated Measures mixed model of $\Delta$ HbA1c to Week 24 with adjustment for baseline eGFR in addition to adjustment for baseline HbA1c (prior to rescue and treatment discontinuation)	Difference in outcome improvement at Week 24 without rescue and without treatment discontinuation.	MAR	No imputation	FAS
ANCOVA of $\Delta$ HbA1c to Week 24 from MI-RD imputation	Difference in outcome improvement at Week 24 regardless of rescue or treatment discontinuation.	MNAR	Observed and Imputed values	RAND
ANCOVA of $\Delta$ HbA1c to Week 24 from washout imputation	Difference in outcome improvement at Week 24 regardless of rescue or treatment discontinuation.	MNAR	Observed and Imputed values	RAND

$\Delta$ HbA1c=change from baseline in HbA1c; PP=Per Protocol; FAS = Full analysis set

a The primary analysis

b The sensitivity analysis on PP will be applied to primary efficacy endpoint only if there will be more than 10% difference in number of patients from FAS

#### 4.2.6.3 Secondary Efficacy Variables

The secondary endpoints, i.e, percent change from baseline in total body weight (using logarithmic transformation) at Week 24, change from baseline in FPG at Week 24, change from baseline in seated SBP at Week 24, will be analyzed using a longitudinal repeated measures analysis, similar to the one used for the primary analysis of the primary endpoint.

Summaries and analyses supporting the secondary efficacy objectives are:

**Table 11 Summary of Analyses to Meet Secondary Efficacy Objectives**

Analysis type	LOCF or Observed values	Analysis set
Repeated measures mixed model of percent change from baseline to Week 24 in body weight (kg) (prior to treatment discontinuation)	Observed values	FAS
Repeated measures mixed model of change from baseline to Week 24 in FPG (mg/dL (prior to rescue and treatment discontinuation)	Observed values	FAS
Repeated measures mixed model of change from baseline to Week 24 in seated SBP (mmHg) (prior to treatment discontinuation)	Observed values	FAS

LOCF = Last Observation carried Forward; FAS = Full analysis set

#### 4.2.6.4 Sequential Testing Procedure

A sequential testing procedure will be employed among the primary endpoint and secondary endpoints in order to control the type I error rate at the 0.05 level. The tests for the secondary efficacy endpoints will be performed only if the test for the primary endpoint is significant, in which case the secondary endpoints will be tested in the order that they appear in the [Table 11](#). Statistical tests will be only performed for a given secondary endpoint if all previous sequential tests for that comparison between dapagliflozin and placebo are also significant. Otherwise, the testing procedure will stop at the secondary endpoint that does not reach statistical significance. If either the testing procedure is stopped or superiority to placebo is not demonstrated, then nominal p-values will be provided.

#### 4.2.6.5 Exploratory Efficacy Variable

CCI

CCI

Table 12 lists the summary of exploratory analyses on continuous endpoints.

**Table 12** Summary of analyses to exploratory analysis on continuous endpoints

Analysis Type	LOCF or observed values	Analysis Set
CCI 		

ANCOVA = Analysis of Covariance; LOCF = Last Observation carried Forward; FAS = Full analysis set

Exploratory analyses of variables that represent proportions of patients will be performed using the methodology as described in Section 4.1.9.

Table 13 lists the summary of exploratory proportion analyses.

**Table 13** Summary of exploratory analysis on categorical endpoints

Analysis Type	LOCF or observed values	Analysis Set
CCI 		

**Table 13** Summary of exploratory analysis on categorical endpoints

Analysis Type	LOCF or observed values	Analysis Set
CCI		

**Table 13** Summary of exploratory analysis on categorical endpoints

Analysis Type	LOCF or observed values	Analysis Set
CCI		

CCI

#### 4.2.6.6 Subgroup Analysis for Efficacy Variables

CCI

**Table 14 Contrast Coefficients for the Example Gender-by-treatment Interaction**

Gender	Male	Male	Female	Female
Treatment group	Dapa 10 mg	Placebo	Dapa 10 mg	Placebo
Contrast coefficient	-1	1	1	-1

Table 15 lists the subgroup variables with the efficacy endpoints.

Subgroup analysis for other efficacy and safety variables will be conducted as deemed appropriate and necessary.

**Table 15 Subgroup analysis for the efficacy variables**

Analysis endpoints	Grouping Variable	Category	Analysis set used
---------------------------	--------------------------	-----------------	--------------------------

**Table 15**      **Subgroup analysis for the efficacy variables**

Analysis endpoints	Grouping Variable	Category	Analysis set used
CCI			

#### **4.2.7 Safety Variables**

The Safety Analysis Set will be used for all safety analyses, including all data after rescue during the double-blind treatment period. Sensitivity analyses on data collected prior to rescue during the double-blind treatment period will be performed for selected Adverse Events (AEs) as described in multiple sub-sections under Section 4.2.7.1.

Safety analyses will be conducted on the double-blind treatment period and follow-up period.

AEs within 4 days or SAEs within 30 days post last double-blind study medication, which are considered in the double-blind treatment period, will not be counted as AEs or SAEs during the follow-up period.

Unless otherwise specified, the safety analyses of changes from baseline to a specific time point in safety variables (e.g., laboratory parameters and vital signs) will only include patients from the Safety Analysis Set who have data available for both the baseline and the time point under consideration.

Safety data that collected before randomization will not contribute to summaries but will be listed.

##### **4.2.7.1 Adverse Events**

Adverse Events (AEs) will be classified by Primary System Organ Class (SOC) and Preferred Term (PT) according to the Medical Dictionary for Regulatory Activities (MedDRA). All adverse events will be coded using the latest available version of MedDRA by the database lock.

Unless otherwise specified, no statistical tests will be performed to compare AE rates between treatment groups. This policy was adopted to recognize the lack of power and the potential for misleading interpretation based on repeated statistical tests which increase the family wise Type I error level.

Counting rules for adverse events are described in Section 4.3.8.

In summaries by system organ class (SOC) and preferred term (PT), AEs will be sorted by decreasing frequency of each PT and SOC, within SOC, according to the Dapagliflozin 10 mg group. In summaries by PT, AEs will be sorted by decreasing frequency of PT according to the Dapagliflozin 10 mg group.

Missing AE dates will be imputed as defined in Section 4.3.3.

Separate pages to capture events of hypoglycemia and to capture all potential events of DKA are contained within the CRF. Discontinuation due to hypoglycemia would not be reported on an AE CRF page unless the event fulfilled criteria for an SAE in which case an SAE form would be completed. Hypoglycemia and DKA events that are reported as SAEs will be included in all summaries of AEs or SAEs (see Section 4.2.7.1.1). Separate summaries will be

provided including hypoglycemia events reported on the hypoglycemia CRF pages (see Section 4.2.7.1.6 Adverse Events of Special Interest).

#### **4.2.7.1.1 All Adverse Events**

All adverse events (serious and non-serious) with onset during the double-blind treatment period will be summarized by system organ class, preferred term and treatment group, for both the primary and sensitivity safety analyses.

The patient incidence of Related AEs, Deaths, SAEs and AEs Leading to Discontinuation of Study Medication (DAEs) will be summarized. Hypoglycemic and DKA events that are reported on separate eCRF pages will be summarized separately.

In addition, following summaries will be provided for the double-blind treatment period. These summaries will exclude hypoglycemic AEs:

- Proportion of patients with adverse events in subgroups of patients defined by age category (< 65 and  $\geq$ 65 yrs), gender, race and female age category ( $\leq$ 50 and >50 yrs).
- Most common adverse events by preferred term and treatment group (reported by  $\geq$ 2% and  $\geq$ 5% of patients in any treatment group).
- Adverse events by system organ class, preferred term, intensity and treatment group.
- Adverse events related to study medication by system organ class, preferred term and treatment group.

All AEs occurring during the study (including the placebo lead-in period, double-blind treatment and the follow-up period) will be listed.

#### **4.2.7.1.2 Deaths**

All deaths recorded on the status page, the AE page, or SAE page (with a death date, cause of death, outcome or SAE categorization present) of the CRF will be considered a death in the analyses. Any deaths that occur during the study will be described in depth as narrative in the CSR. A listing of all deaths that occur during the study will be produced.

#### **4.2.7.1.3 Serious Adverse Events**

SAEs (including hypoglycemic and DKA events) with an onset from Day 1 of double-blind treatment up to and including 30 days after the last dose date in the double-blind treatment period will be considered as occurring during the double-blind treatment period.

SAEs (including hypoglycemic and DKA events) occurring during the double-blind treatment period will be summarized by SOC, PT and treatment group. In addition, the proportion of patients with related SAEs will be presented by SOC, PT and treatment group.

A listing of all SAEs will be produced, displaying all SAEs (including pre-treatment events) that occurred during the study.

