6.1 Definition of adverse events

An AE is the development of an undesirable medical condition or the deterioration of a pre-existing medical condition following or during exposure to a pharmaceutical product, whether or not considered causally related to the product. An undesirable medical condition can be symptoms (e.g., nausea, chest pain), signs (e.g., tachycardia, enlarged liver) or the abnormal results of an investigation (e.g., laboratory findings, electrocardiogram). In clinical studies, an AE can include an undesirable medical condition occurring at any time, including run-in or washout periods, even if no study treatment has been administered.

The term AE is used to include both serious and non-serious AEs.

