6.3.3 Variables

The following variables will be collect for each AE;

- AE (verbatim)
- The date when the AE started and stopped
- Maximum intensity
- Whether the AE is serious or not
- Investigator causality rating against the IP (yes or no)
- Action taken with regard to investigational product
- Outcome.

In addition, the following variables will be collected for SAEs:

- Date AE met criteria for serious AE
- Date Investigator became aware of serious AE
- AE is serious due to
- Date of hospitalisation
- Date of discharge
- Probable cause of death

- Date of death
- Autopsy performed
- Causality assessment in relation to Study procedure(s)
- Description of AE.

Maximum intensity will be graded according to the following rating scale:

- Mild (awareness of sign or symptom, but easily tolerated)
- Moderate (discomfort sufficient to cause interference with normal activities)
- Severe (incapacitating, with inability to perform normal activities)

It is important to distinguish between serious and severe AEs. Severity is a measure of intensity whereas seriousness is defined by the criteria in Section 6.2. An AE of severe intensity need not necessarily be considered serious. For example, nausea that persists for several hours may be considered severe nausea, but not a SAE unless it meets the criteria shown in Section 6.2. On the other hand, a stroke that results in only a limited degree of disability may be considered a mild stroke but would be a SAE when it satisfies the criteria shown in Section 6.2.

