#### **4.2.7.1.5 Adverse Events Leading to Discontinuation (DAE)**

AEs with an onset during the double-blind treatment period reported with an action taken of discontinuation of study medication will be summarized by SOC, PT and treatment group.

When summarizing AEs leading to discontinuation, no upper cutoff day windows (i.e. 4 days and 30 days from last dosing date in double-blind treatment period for AEs and SAEs respectively) are applied. For double-blind period analyses, the only upper cutoff date is the last date of the double-blind treatment period.

In addition, a patient listing of discontinuation due to AEs will be provided, displaying all events that led to discontinuation that occurred during the study.

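### The onset-date rule in SAP 4.2.7.1.5 can leave a lead-in AE that later stops double-blind drug out of the by-arm discontinuation table, and 4.2.7.1.3 can do the same for an AE that becomes serious

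*SAP*

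**What the plan says.** **Discontinuation AEs.** SAP 4.2.7.1.5 tabulates by arm "AEs with an onset during the double-blind treatment period reported with an action taken of discontinuation of study medication". It drops the usual 4-day and 30-day windows after last dose, but only at the upper end: "For double-blind period analyses, the only upper cutoff date is the last date of the double-blind treatment period". The onset condition at the lower end stays.

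**Serious AEs.** SAP 4.2.7.1.3 assigns to the double-blind period "SAEs (including hypoglycemic and DKA events) with an onset from Day 1 of double-blind treatment", up to 30 days after the last dose. It then states that "SAEs (including hypoglycemic and DKA events) occurring during the double-blind treatment period will be summarized by SOC, PT and treatment group". SAP 4.3.3 uses the onset date, imputed where missing for non-serious AEs, to put an event into an analysis period.

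**Before randomization.** Protocol 6.3.1 starts AE collection at Visit 2, when the 4-week placebo lead-in begins. SAP 4.2.7 adds: "Safety data that collected before randomization will not contribute to summaries but will be listed".

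**What is recorded.** Protocol 6.3.3 gives each AE one start date, one stop date, one maximum intensity and the action taken with study drug. For SAEs it also collects "Date AE met criteria for serious AE". No SAP rule uses that date to assign a period.

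**Deterioration.** Protocol 6.1 includes in its definition of an AE "the deterioration of a pre-existing medical condition following or during exposure to a pharmaceutical product". Protocol 6.3.6 adds rules for reporting laboratory values, vital signs and examination findings that have worsened since baseline.

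**The concern.** An event that starts in the lead-in and is still ongoing at randomization has a start date before Day 1. If it later becomes serious, or leads the patient to stop drug, that step happens on randomized treatment. It is the part of the event's course that could differ between arms. A rule that looks only at the start date treats the whole record as pre-treatment.

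Safety in this trial is assessed through descriptive summaries by treatment group, without tests (Protocol 8.5.7, SAP 3.4). The by-arm tables are therefore the main comparison. Listings show the event but give no rate per arm. Any omission of this kind lowers the count, never raises it.

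Two features suggest an oversight. Section 4.2.7.1.5 goes out of its way to widen the upper end of the discontinuation window. For laboratory data, SAP 4.2.7.2.1 has an explicit worsening rule: a value already beyond the limit at baseline counts again if it becomes more extreme. Adverse events have no equivalent.

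**Working it through.** The plan states no figure on this point, so there is none to reproduce. The check applies the rules to test records.

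**Notation (study days).** o = AE onset; s = day the AE met serious criteria; d = day double-blind drug was stopped; L = last dose day, set to d if drug was stopped and to 168 otherwise; E = last day of the double-blind period, set to 169 (the Week 24 target day).

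**Rules as written**
- SAE table (4.2.7.1.3 with 4.3.3): include if 1 ≤ o ≤ L + 30.
- Discontinuation table (4.2.7.1.5): include if 1 ≤ o ≤ E and the action taken was discontinuation.

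**Rules under the proposed change**
- SAE table: include if o or s lies from 1 to L + 30, unless s is before Day 1.
- Discontinuation table: include if the action taken was discontinuation of double-blind drug, whatever o is.

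| Record | o | s | d | SAE, as written | SAE, changed | Discontinuation, as written | Discontinuation, changed |
|---|---|---|---|---|---|---|---|
| A | -10 | 20 | 20 | out | in | out | in |
| B | -1 | 5 | 6 | out | in | out | in |
| C | 10 | 20 | 20 | in | in | in | in |
| D | -10 | -5 | none | out | out | not applicable | not applicable |

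For record A, L = 20, so the SAE window is Day 1 to Day 50. Onset on Day -10 fails it; meeting serious criteria on Day 20 passes. C is unaffected by the change. D was already serious before Day 1 and rightly stays out.

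**Two conditions that change record A**
1. If SAE onset means the day the event became serious, the existing SAE rule tests s = 20 and record A is already in. The discontinuation result does not change, because section 4.2.7.1.5 names the onset of the AE.
2. If the site reports the worsening as a new AE starting on Day 20, then o = 20 and the event enters both tables as the rules stand.

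A non-serious lead-in AE that stops drug is affected only in the discontinuation table.

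**Disposition.** SAP 4.2.1 counts patients by reason for discontinuation with no onset condition. A patient like A, recorded as stopping for an AE, is counted there and not in the discontinuation AE table.

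**Scale.** Planned arm size is 302 / 2 = 151 (SAP 1.4). One missed patient is 1/151 = 0.66%, about 0.7 percentage points. The documents give no frequency for such events. If 1 to 5 patients in an arm were affected (an assumption made only to show scale), that arm's percentage would be too low by 1/151 = 0.7 to 5/151 = 3.3 points. With a 4-week lead-in, the low end is more plausible.

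**The case against.** The strongest reply is that the omission depends on how sites keep records. Protocol 6.1 makes deterioration an AE in its own right. Under Protocol 6.3.6, worsening since baseline in mandated laboratory values, vital signs and other safety variables is reportable if it is clinically significant, meets a seriousness criterion or is why treatment stopped. Visit 4 laboratory values are the baseline. Much on-drug worsening of eGFR, other laboratory values or blood pressure could therefore get its own on-treatment record. This stands, and it narrows the gap considerably. It does not close it, because neither document requires a new record when an AE already on file worsens. The CRF completion instructions mentioned in Protocol section 5 might do so, but they are not among the documents.

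The SAE wording is also open. Protocol 6.2 defines an SAE as an AE that meets a seriousness criterion, so its onset could be the day it became serious. SAP 4.3.3 points the other way but does not define SAE onset. That half is an ambiguity with a likely reading. The sentence in SAP 4.2.7 on pre-randomization data settles nothing, since seriousness or stopping on Day 20 is recorded after randomization.

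The events are not hidden. The SAE listing includes pre-treatment events, the discontinuation listing covers all events that led to stopping, and deaths have no onset window. No test or decision rule depends on these tables. Randomization should balance ongoing lead-in events at Day 1, although it does not balance what treatment then does to them.

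**Conclusion.** The point holds in limited form. For discontinuation AEs the rule is explicit: a lead-in AE kept as one record that later stops double-blind drug is missing from the by-arm table. For SAEs the same follows on the more natural reading of 4.2.7.1.3 with 4.3.3. Each missed patient is about 0.7% of an arm of 151. How many there would be is unknown, and probably few. Severity is minor.

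A reader might infer more than the documents support:
- That every such event is lost. The omission needs a single record with a lead-in start date, and it is from the summary tables, not from reporting.
- That the discontinuation and disposition tables must disagree. They will on this account only if such a patient exists. They can differ anyway, because they use different sources and SAP 4.2.7.1 keeps non-serious hypoglycemia discontinuations off the AE page.
- That a definite share of the discontinuation table is missing. This would need rates for lead-in AEs, for those still ongoing and for those that escalate, and the documents give none. Events that became serious without stopping drug would also have to be kept out of that ratio.
- That the site instructions are deficient. They cannot be judged from these documents.

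**What to change.** Make two edits to the SAP:

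1. **Section 4.2.7.1.5.** Count every AE whose action taken was discontinuation of double-blind study drug, whatever its onset date.
2. **Section 4.2.7.1.3.** Place an SAE in the double-blind period if its onset, or the date collected as "Date AE met criteria for serious AE", falls from Day 1 to 30 days after last dose. State that an SAE already serious before Day 1 stays out. This also settles which date SAE onset means.

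Both edits use fields the protocol already collects, so the cost is two changes of wording and the matching program logic. The downside is that SAE and discontinuation counts may rise slightly.

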#### **4.2.7.1.4 Related Adverse Events**

The patient incidence of related AEs will be presented by SOC, PT and treatment group.

#### **4.2.7.1.5 Adverse Events Leading to Discontinuation (DAE)**

AEs with an onset during the double-blind treatment period reported with an action taken of discontinuation of study medication will be summarized by SOC, PT and treatment group.

When summarizing AEs leading to discontinuation, no upper cutoff day windows (i.e. 4 days and 30 days from last dosing date in double-blind treatment period for AEs and SAEs respectively) are applied. For double-blind period analyses, the only upper cutoff date is the last date of the double-blind treatment period.

In addition, a patient listing of discontinuation due to AEs will be provided, displaying all events that led to discontinuation that occurred during the study.

#### **4.2.7.1.6 Adverse Events of Special Interest**

Separate summaries will be provided for the following adverse events of special interest. To identify each type of adverse event of special interest in this section, a list of preferred terms will be selected, reviewed and finalized prior to the database lock and unblinding of the database.

- Genital Infection
- Urinary-tract Infection
- Volume depletion (including hypotension, dehydration, and hypovolemia)
- Renal Impairment/Renal Failure
- Bone Fractures

Unless otherwise specified, AEs and SAEs of special interest with an onset from Day 1 of double-blind treatment up to and including 4 days and 30 days respectively, after the last dose date in the double-blind treatment period will be considered as occurring during the double-blind treatment period.

